**Model:**

Denote spending for member  $i$  at time  $t$  as  $y_{it}$ , with  $i \in \{1, \dots, N\}$ ,  $t \in \{-23, \dots, 0, \dots, 36\}$ , and  $N$  the number of members. Let  $M$  be the number of covariates included in the model and  $x_{m,it}$  denote the  $m^{\text{th}}$  covariate for member  $i$  at month  $t$ .

Then the two-stage model is:

$$\begin{aligned} p_{it} &\sim \text{Bernoulli}(\theta_{it}), \\ \text{logit}(\theta_{it}) &= \alpha_0 + \sum_{m=1}^M \alpha_m x_{m,it}, \\ (y_{it} \mid y_{it} > 0) &\sim \text{Poisson}(\mu_{it}), \quad \text{and} \\ \mu_{it} &= E(y_{it} \mid y_{it} > 0, X_i), \end{aligned}$$

where  $X_i$  is the matrix for all observed covariates for member  $i$ . We model the mean,  $\mu_{it}$ , as

$$\log(\mu_{it}) = \beta_0 + \sum_{m=1}^M \beta_m x_{m,it}.$$

We suppose,

$$\begin{aligned} \sum_{m=1}^M \alpha_m x_{m,it} &= \alpha_1 E4_i + \alpha_2 post_{it} + \alpha_3 month_{it} + \alpha_4 E4_i * post_{it} + \alpha_5 E4_i * month_{it} + \\ &\quad \alpha_6 post_{it} * month_{it} + \alpha_7 E4_i * post_{it} * month_{it} + \alpha_8 Age_i + \\ &\quad \alpha_9 Gender_i + \alpha_{10} Elixhauser_i + \alpha_{11} Relationship_i + \\ &\quad \alpha_{12} FundingType_i + \alpha_{13} ACSPopulation_i + \alpha_{14} ACSIncome_i + \\ &\quad \alpha_{15} ACSPercentWhite_i + \alpha_{16} ACSEducation_i, \end{aligned}$$

and

$$\begin{aligned} \sum_{m=1}^M \beta_m x_{m,ijt} &= \beta_1 E4_i + \beta_2 post_{it} + \beta_3 month_{it} + \beta_4 E4_i * post_{it} + \beta_5 E4_i * month_{it} + \\ &\quad \beta_6 post_{it} * month_{it} + \beta_7 E4_i * post_{it} * month_{it} + \beta_8 Age_i + \\ &\quad \beta_9 Gender_i + \beta_{10} Elixhauser_i + \beta_{11} Relationship_i + \\ &\quad \beta_{12} FundingType_i + \beta_{13} ACSPopulation_i + \beta_{14} ACSIncome_i + \\ &\quad \beta_{15} ACSPercentWhite_i + \beta_{16} ACSEducation_i, \end{aligned}$$

for member  $i$  where:

- $E4_i$  = indicator of whether the  $i^{\text{th}}$  member is enrolled in VBF-E4
- $post_{it}$  = indicator of whether the  $i^{\text{th}}$  member is in the post index period,  $t \geq 1$
- $month_{it}$  = time in months from the  $i^{\text{th}}$  members index date
- $Age_i$  = centered age for the  $i^{\text{th}}$  member at index
- $Gender_i$  =  $i^{\text{th}}$  members gender at index
- $Elixhauser_i$  = Elixhauser comorbidity score for member  $i$  at index
- $Relationship_i$  =  $i^{\text{th}}$  members relationship to contract holder at index
- $FundingType_i$  =  $i^{\text{th}}$  members funding type at index
- $ACSPopulation_i$  = ACS population at the zip code level for member  $i$  at index

- $ACSIncome_i$  = ACS median household income in the prior 12 months at zip code level for member  $i$  at index
- $ACSPercentWhite_i$  = ACS percent of white people at the zip code level for member  $i$  at index
- $ACSEducation_i$  = ACS percent of people 25 years or older with a Bachelor's degree in the prior 12 months at the zip code level for member  $i$  at index

**Missing Data:**

Complete-case analyses.

## **Aim 2 Statistical Analysis Plan**

**Aim 2:** Assess impact of VBF-e on patient out-of-pocket spending and health plan spending for prescription drugs and non-drug medical care.

**Study Design:** Difference in Differences

**Study Period:** Jan 1st, 2015 – December 31st, 2019

**Unit of Analysis:** per member month

**Analytic Sample:** Premera Blue Cross beneficiaries less than 65 years of age

**Censoring Events:**

*Month at which an individual:*

- disenrolled for more than 1 month during study period
- turned 65 years of age

*Administrative censoring at:*

- end of study period (December 31st, 2019)

*Administrative left truncation at:*

- 24 months prior to index date

**Exclusion criteria:**

*Exclude individuals with:*

- missing gender information
- missing zip code level demographics at all member months

**Inclusion criteria:**

*Individuals:*

- aged 0-64
- Continuously enrolled in an employer-sponsored health plan for at least 12 months (with one-month allowable gap) prior to the index date
  - For individuals in the exposed group, the index date is defined as the start date of value-based formulary implementation at the employer group level
  - For individuals in the control group, the index date is defined as the index date of the matched exposed individual

*Employer groups:*

- that transition to the value-based formulary if they transitioned **all** enrollees in that employer group (no individual selection)

**Outcomes:**

*Primary outcome(s):* change in area under the curve one year after index date for all outcomes

*Secondary outcome(s):* change in area under the curve 2 and 3 years after index date for all outcomes

*Actual outcome list:*

- Total spending for prescription drugs
- Patient out-of-pocket spending for prescription drugs
- Health plan spending for prescription drugs
- Total healthcare spending
- Total health plan and patient spending for vision

**Exposure:** VBF-E4 and non-VBF-E4

**Covariates:**

*Adjustment variables:*

| Covariates   | Time of Measurement                     | Notes  | Specification  |
|--|---|--|--|
| Gender   | Month before E4 transition = index time |  | Indicator  |
| Age  | Index time                              | Centered   | Continuous   |
| Relationship to contract holder                        | Index time                              |  | Categorical 

• Contract Holder,

• Dependent,

• Spouse/Domestic Partner)

 |
| ACS  | Index time (or closest to this)         | For individuals with missing ACS variables at index time, set to closest observed value. | Quintile   |
| Percent 25 years old or older with a bachelor's degree |   |  | Quintile   |
| Median household income                                |   |  | Quintile   |
| Population size  |   |  | Quintile   |
| Percent White  |   |  | Quintile   |
| Funding Type   | Index time                              |  | Categorical (self, full)   |
| Elixhauser   | 12 months prior to transition time      |  | Categorical variable 

• 0

• 1

   |

|                      |                     |   |   |
|----------------------|---------------------|---|---|
|                      |                     |   | • >=2   |
| Time from index date | At all observations | 0 = index time, 1 = E4 transition month                           | Continuous (-23 to 36)  |
| Post                 | At all observations | Indicator for post period   | indicator   |
| Seasonality          | At all observations | Adjust for calendar year and separately adjust for calendar month | Categorical (1 through 12 for elig_mth) and (2015 through 2019 for elig_yr) |

**Effect Modifiers:** None.

**Exploratory Data Analysis:**

- Plot outcomes across time across all index times
- 12-month enrollment for patient member months
- Histogram of age
- Univariate statistics, bivariate
- Conduct a Table 1
- Loss to follow-up

**Statistical Analyses:**

We will use a DID approach to study the impact of the E4 transition and generalized linear models to model the impact of the E4 transition via changes in outcomes. Time will be anchored at the month prior to the transition (e.g., index time is set to the month prior to the transition) for the E4 group. Each of the E4 transition members will be matched to two controls via propensity score methods. Non-E4 transition members will be assigned to an index date corresponding to their E4 transition match. We will not adjust for the matching in our models.

To match controls to E4 members, we will model the propensity score based on covariates we believe may be related to exposure: Gender, ACS Population Size, ACS Household Income in past 12 months, ACS Percent 25 years and older with a Bachelor's degree, ACS Percent White, and Year of birth. Then, we will obtain the log odds (logit) of the fitted values (e.g., estimates) of the propensity score for everyone (both E4 and possible controls) and order the log odds of the treatment (E4) group from largest to smallest (in decreasing order). For each E4 member, we will find the two nearest neighbor controls, e.g., the controls with the closest propensity score to that of the E4 individual with 12 months of continuous prior enrollment at the E4 individual's index date. After completing matching, we will check for covariate balance across groups based on the standardized mean differences and Kolmogorov–Smirnov statistic.

To address the zero-inflated and right skewed nature of the cost outcomes, we will use a two part-model. In the first stage of the two-part model, we will estimate the probability of the response being greater than zero and in the second stage we will model the non-zero portion. We will choose the most appropriate mean-variance relationship by performing goodness-of-fit tests (Pearson's correlation, Pregibon link, modified Park, and modified Hosmer-Lemeshow tests) on the primary cost outcome. We will assume independence in the mean modeling to estimate the area under the curve change at 1 (primary), 2 and 3 years after index, and use the cluster bootstrap to obtain standard errors that account for repeated measurements within an individual (clustering on the individual level). We will adjust for

individual-level (age, gender, and Elixhauser comorbidity score) and census ZIP-code level characteristics (educational attainment, median household income, race/ethnicity and urban residence) in all models.

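### Matched controls share the E4 member's index date but need not share its benefit-year start month, so a within-year cost-sharing cycle could appear as a formulary effect on Aim 2 drug spending

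*SAP*

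**What the plan says.** For exposed members, the Aim 2 Inclusion criteria state that "the index date is defined as the start date of value-based formulary implementation at the employer group level". Time is coded "0 = index time, 1 = E4 transition month".

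Controls are chosen under Aim 2 Statistical Analyses: "we will model the propensity score based on covariates we believe may be related to exposure: Gender, ACS Population Size", followed by three more ZIP-level census variables and year of birth. A control must also be someone "with 12 months of continuous prior enrollment" at the E4 member's index date. Then "Non-E4 transition members will be assigned to an index date corresponding to their E4 transition match". No employer or plan variable enters the match. Funding type is an adjustment covariate only.

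The seasonality row of the Covariates table reads "Adjust for calendar year and separately adjust for calendar month". These terms do not vary by group, and the Model equations omit them. The equations give E4 members their own linear time slope before the transition, and their own level and slope change after it.

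The Aim 2 outcomes include "Patient out-of-pocket spending for prescription drugs" and plan spending on drugs. The primary measure is the one-year change in area under the curve (AUC).

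**The concern.** Sharing an index date aligns calendar time within a matched set. It does not align where each person stands in the benefit year. If a deductible or similar feature makes out-of-pocket spending high early in the benefit year and low late, a control whose plan renews in another month is out of phase with its E4 match. Calendar-month terms common to both groups cannot absorb a cycle that falls in different calendar months for different people.

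The straight-line time terms make this matter. If E4 members all renew at t=1, their pre-index months are two complete falling cycles. A straight line through them slopes down although the yearly average is flat, and the model carries that slope past t=0. The reset at t=1 then looks like a rise in out-of-pocket spending and, by the mirror image, a fall in plan-paid spending. That is a shift of cost from plan to patient, which Aim 2 is there to measure, and it would reach the primary one-year results.

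**Working it through.** The SAP gives no figure to reproduce, so the check asks what its mean model returns when the true effect is zero.

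**From the SAP:** months t=-23 to 36; log link; E4, post, month and all their interactions; two controls per E4 member; t=1 as the transition month.

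**Assumed:** all E4 members renew at t=1. Mean spending in benefit month k (0 to 11) is 1 + d(5.5 - k)/11, so d is the total fall over the year as a share of the mean. A share a of controls renews in the same month, and the rest are spread evenly over the other 11 months. AUC change is the E4 prediction with, versus without, the E4-by-post and E4-by-post-by-month terms.

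**By hand, straight-line approximation**

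1. Each 12-month cycle contributes 143 to the within-cycle sum of squares of time. The full sums are (24³ - 24)/12 = 1150 for the 24 pre months and (36³ - 36)/12 = 3885 for the 36 post months.
2. The pre-index slope is -(d/11)(286/1150). Carried 18 months, from the pre-period centre (-11.5) to the centre of year one (6.5), it puts the counterfactual 0.407d below the true mean.
3. The post slope is -(d/11)(429/3885). At 6.5, 12 months before the post-period centre (18.5), the fitted line is 0.120d above the mean.
4. The false gap for E4 is 0.407d + 0.120d = 0.527d.
5. Controls show the same pattern scaled by a - (1 - a)/11, so (1 - a)(12/11) of it is left over.
6. Bias is about 0.527 × (12/11) × d(1 - a) = 0.575 d(1 - a).

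**Against the Gamma log-link fit, one year, out-of-pocket**

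| Depth d | Aligned share a | By hand | Fitted |
|---|---|---|---|
| 20% | 90% | 0.575 × 0.2 × 0.10 = +1.2% | +1.2% |
| 40% | 75% | 0.575 × 0.4 × 0.25 = +5.8% | +6.0% |
| 60% | 60% | 0.575 × 0.6 × 0.40 = +13.8% | +15.2% |

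Adding common calendar-month terms changes the fitted values by less than 0.1 point.

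**Plan-paid, rising 20% over the year (d = -20%):** fitted bias runs from -1.1% (a = 90%) to -4.5% (a = 60%). By hand it runs from -1.2% to -4.6%.

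**Other definition of AUC change:** a plain difference of pre and post averages of the fitted curves gives +0.2% to +3.0%. A comparison of observed means 12 months before and 12 months after gives zero, because each window holds one whole cycle.

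**Shorter history:** members need only 12 months of prior enrolment. Cutting the pre-period to 12 months for everyone raises the three fitted values to +2.7%, +14.7% and +39.9%. This is an extreme case, since many members would have longer history.

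**Remedies:** with equal cycle depth in both groups, alignment of all controls gives 0.0%, and so do benefit-month terms. With depth 40% in E4 and 20% in controls, alignment and common benefit-month terms together still leave +11.2% (by hand 0.527 × 0.20 = 10.5%). With 60% against 40% they leave +11.5%. Terms that differ by group absorb a stable cycle of either depth.

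**The case against.** The strongest objection is that the SAP says nothing about renewal months, deductibles or whether a formulary starts at renewal. A reader might infer that controls are known to be at another point of their benefit year. The text does not support that, nor does it exclude it. Matched sets share calendar months, so if employers renew in a common month and the cycles are equally deep, the cycle cancels exactly. The study period and the time grid are both 60 months, so the full window from -23 to 36 exists only for a January 2017 transition. That is compatible with January starts but does not establish them. This objection stands, and the point is therefore conditional.

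Second, the size depends on how AUC change is computed, which the SAP leaves open. The larger figures need an extrapolated counterfactual. This also stands. However, an E4-specific slope and break make the extrapolated contrast a natural reading of the model.

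Third, a reader might extend the point to any other benefit change an employer makes at renewal. The documents mention no such change, and aligning start months would not remove it: in the same fit, a 5%, 10% or 20% step confined to E4 members passes through as a 5%, 10% or 20% effect. It is a separate matter and no part of this finding.

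Fourth, the matching text is the same in Aims 1 and 3, which might suggest equal harm there. No magnitude has been worked out for days supply or visits, and none is claimed.

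**Conclusion.** The point holds in conditional form. The plan neither aligns nor adjusts for benefit-year position, and its listed calendar terms cannot do so. If transition occurs at renewal, cost-sharing cycles within the year and some controls renew in other months, the segmented linear model produces a false one-year change. Under the stated scenarios this is about +1% to +15% for out-of-pocket drug spending and about -1% to -4.5% for plan-paid spending at 20% depth.

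These figures are illustrative. Depth and aligned share are assumed, only the mean part of the two-part model was fitted, and the contrast is against the extrapolated E4 counterfactual. No remedy should be credited with zero bias unconditionally, because that result needs equal cycle depth or group-specific terms. The change is worth making because the bias runs in the direction of the cost shift under study and the remedy is cheap.

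**What to change.** In the Aim 2 matching step, do one of two things:

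- Match controls exactly on benefit-year start month, taking the nearest propensity score within that month.
- Add month of the benefit year (1 to 12, categorical) to both model parts, beside calendar month. Let it differ by group if cycle depth differs. If depth differs, matching alone is not enough and the group-specific terms are needed.

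In either case, state when the participating employers' benefit years start, show start month in the balance table, and write the seasonal terms into the Model equations.

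The cost is SAP wording and one employer-level field, assumed to be in the insurer's group file. Exact matching also shrinks the control pool for uncommon renewal months. Benefit-month terms assume that the cycle keeps its shape after the transition, which the plan should acknowledge. If all groups prove to renew in one month, exact matching costs almost nothing.

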**Model:**

Denote spending for member  $i$  at time  $t$  as  $y_{it}$ , with  $i \in \{1, \dots, N\}$ ,  $t \in \{-23, \dots, 0, \dots, 36\}$ , and  $N$  the number of members. Let  $M$  be the number of covariates included in the model and  $x_{m,it}$  denote the  $m^{\text{th}}$  covariate for member  $i$  at month  $t$ .

Then the two-stage model is:

$$\begin{aligned} p_{it} &\sim \text{Bernoulli}(\theta_{it}), \\ \text{logit}(\theta_{it}) &= \alpha_0 + \sum_{m=1}^M \alpha_m x_{m,it}, \\ (y_{it} | y_{it} > 0) &\sim \text{Gamma}(a, b_{it}), \end{aligned}$$

with  $a$  as the shape parameter and  $b$  as the rate parameter of the Gamma distribution, and

$$\mu_{it} = E(y_{it} | y_{it} > 0, X_i) = \frac{a}{b_{it}},$$

where  $X_i$  is the matrix for all observed covariates for member  $i$ . We model the mean,  $\mu_{it}$ , as

$$\log(\mu_{it}) = \beta_0 + \sum_{m=1}^M \beta_m x_{m,it}.$$

We suppose,

$$\begin{aligned} \sum_{m=1}^M \alpha_m x_{m,it} &= \alpha_1 E4_i + \alpha_2 post_{it} + \alpha_3 month_{it} + \alpha_4 E4_i * post_{it} + \alpha_5 E4_i * month_{it} + \\ &\quad \alpha_6 post_{it} * month_{it} + \alpha_7 E4_i * post_{it} * month_{it} + \alpha_8 Age_i + \\ &\quad \alpha_9 Gender_i + \alpha_{10} Elixhauser_i + \alpha_{11} Relationship_i + \\ &\quad \alpha_{12} FundingType_i + \alpha_{13} ACSPopulation_i + \alpha_{14} ACSIncome_i + \\ &\quad \alpha_{15} ACSPercentWhite_i + \alpha_{16} ACSEducation_i, \end{aligned}$$

and

$$\begin{aligned} \sum_{m=1}^M \beta_m x_{m,it} &= \beta_1 E4_i + \beta_2 post_{it} + \beta_3 month_{it} + \beta_4 E4_i * post_{it} + \beta_5 E4_i * month_{it} + \\ &\quad \beta_6 post_{it} * month_{it} + \beta_7 E4_i * post_{it} * month_{it} + \beta_8 Age_i + \\ &\quad \beta_9 Gender_i + \beta_{10} Elixhauser_i + \beta_{11} Relationship_i + \\ &\quad \beta_{12} FundingType_i + \beta_{13} ACSPopulation_i + \beta_{14} ACSIncome_i + \\ &\quad \beta_{15} ACSPercentWhite_i + \beta_{16} ACSEducation_i, \end{aligned}$$

for member  $i$  where:

- $E4_i$  = indicator of whether the  $i^{\text{th}}$  member is enrolled in VBF-E4
- $post_{it}$  = indicator of whether the  $i^{\text{th}}$  member is in the post index period,  $t \geq 1$

- $month_{it}$  = time in months from the  $i^{th}$  members index date
- $Age_i$  = centered age for the  $i^{th}$  member at index
- $Gender_i$  =  $i^{th}$  members gender at index
- $Elixhauser_i$  = Elixhauser comorbidity score for member  $i$  at index
- $Relationship_i$  =  $i^{th}$  members relationship to contract holder at index
- $FundingType_i$  =  $i^{th}$  members funding type at index
- $ACSPopulation_i$  = ACS population at the zip code level for member  $i$  at index
- $ACSIncome_i$  = ACS median household income in the prior 12 months at zip code level for member  $i$  at index
- $ACSPercentWhite_i$  = ACS percent of white people at the zip code level for member  $i$  at index
- $ACSEducation_i$  = ACS percent of people 25 years or older with a Bachelor's degree in the prior 12 months at the zip code level for member  $i$  at index

**Missing Data:**

Complete-case analyses.

### **Aim 3 Statistical Analysis Plan**

**Aim 3:** Assess impact of VBF-e on the number of emergency department visits, number of outpatient visits, and number of days in hospital.

**Study Design:** Difference in Differences

**Study Period:** Jan 1st, 2015 – December 31st, 2019

**Unit of Analysis:** per member month

**Analytic Sample:** Premera Blue Cross beneficiaries less than 65 years of age

**Censoring Events:**

*Month at which an individual:*

- disenrolled for more than 1 month during study period
- turned 65 years of age

*Administrative censoring at:*

- end of study period (December 31st, 2019)

*Administrative left truncation at:*

- 24 months prior to index date

**Exclusion criteria:**

*Exclude individuals with:*

- missing gender information
- missing zip code level demographics at all member months

**Inclusion criteria:**

*Individuals:*

- aged 0-64
- Continuously enrolled in an employer-sponsored health plan for at least 12 months (with one-month allowable gap) prior to the index date
  - For individuals in the exposed group, the index date is defined as the start date of value-based formulary implementation at the employer group level
  - For individuals in the control group, the index date is defined as the index date of the matched exposed individual

*Employer groups:*

- that transition to the value-based formulary if they transitioned **all** enrollees in that employer group (no individual selection)

**Outcomes:**

*Primary outcome(s):* change in area under the curve one year after index date for all outcomes

*Secondary outcome(s):* change in area under the curve 2 and 3 years after index date for all outcomes

*Actual outcome list:*

Number of emergency department visits

Number of days in hospital

Number of outpatient visits

**Exposure:** VBF-E4 and non-VBF-E4

**Covariates:**

*Adjustment variables:*

| Covariates   | Time of Measurement                     | Notes  | Specification  |
|--|---|--|--|
| Gender   | Month before E4 transition = index time |  | Indicator  |
| Age  | Index time                              | Will be centered.  | Continuous   |
| Relationship to contract holder                        | Index time                              |  | Categorical 

• Contract Holder,

• Dependent,

• Spouse/Domestic Partner)

 |
| ACS  | Index time (or closest to this)         | For individuals with missing ACS variables at index time, set to closest observed value. | Quintile   |
| Percent 25 years old or older with a bachelor's degree |   |  | Quintile   |
| Median household income                                |   |  | Quintile   |
| Population size  |   |  | Quintile   |
| Percent White  |   |  | Quintile   |
| Funding Type   | Index time                              |  | Categorical (self, full)   |
| Elixhauser   | 12 months prior to transition time      |  | Categorical variable 

• 0

• 1

• >=2

                                  |
| Time from index date                                   | At all observations                     | 0 = index time, 1 = E4 transition month  | Continuous (-23 to 36)   |

|             |                     |   |   |
|-------------|---------------------|---|---|
| Post        | At all observations | Indicator for post period   | indicator   |
| Seasonality | At all observations | Adjust for calendar year and separately adjust for calendar month | Categorical (1 through 12 for elig_mth) and (2015 through 2019 for elig_yr) |

**Effect Modifiers:** None.

